General Analytic Strategies. We will examine all variables to determine if parametric distributional assumptions are valid (e.g., normality for the continuous variables). Variables not meeting approximate distributional assumptions will either be transformed or modeled using nonparametric methods. In addition, we will explore the variability and correlation structure of the CHD outcome variables and PTSD symptom severity. Evidence of imbalance in baseline demographic (age, gender, veteran/civilian status) or clinical (high blood pressure, diabetes, major depression) characteristics will be noted and discussed as to whether they are clinically significant and we will consider sensitivity analyses including these covariates in models (models described below separately for each aim), as recommended by the Committee for Proprietary Medicinal Products guidelines (Committee for Proprietary Medicinal Products, 2004). We will also minimize the imbalance on variables known to be related to the predictor and outcome variables by stratifying randomization by gender, age, and major depressive disorder. As the main goal of the aims for this study is to understand how changes in PTSD symptom severity impact changes in CHD markers, we will conduct both an intent-to-treat analysis where participants will be analyzed as part of the group to which they are randomized, regardless of intervention adherence, and a per-protocol or as-treated analysis to strengthen the evidence that the mechanism for the effects of CPT-C vs. control on CHD markers is through PTSD symptom severity changes.

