treatment group: $C = \gamma_0 + \gamma_1^*$ treatment. We then fit a model examining the relationship between the mediator and post-treatment change in CHD biomarkers (Y): Y = β_0 + treatment* β_1 + C* β_2 . Finally, to show mediation, we will test that the product of γ_1 and β_2 is not equal to 0 using an extension of the Sobel first-order test (Fritz & MacKinnon, 2007); that is, the the effects of CPT-C on CHD risk biomarkers are attributable to its effects on PTSD symptom improvement. To fully understand these relationships, we will also investigate the MacArthur approach, where our second model will be (Y): Y = β_0 + treatment* β_1 + C* β_2 + C* treatment * β_3 . Under this approach, improvements in CHD biomarkers are attributable to improvements in PTSD symptoms if there is evidence that γ_1 is not equal to 0, and either β_2 or β_3 are not equal to zero. The model will also be adjusted for stratification variables of gender, age, and major depressive disorder, and as detailed above in the general analytic section in the sensitivity analysis, we will evaluate and include other potentially important covariates, including change in anxiety and depressive symptoms estimated from the changes in HADS anxiety and depression following the intervention. We will also explore an as-treated analysis to maximize the potential mediation effects of PTSD symptom severity changes over time. For these analyses, data will be deemed usable for any individual who drops out of the study after two weeks or more of CPT-C or WP-CON, if PTSD symptom change is available and a repeat CHD biomarker assessment can be performed after the PTSD symptom change is assessed.

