Aim 3: To explore potential moderators of the effects of PTSD symptom severity changes on CHD risk biomarkers. Although there is evidence that PTSD increases CHD risk irrespectively of demographics or trauma characteristics, there is some evidence that the causal pathway underlying the CHD risk may differ with gender and with depression. Consequently, improvement in PTSD symptoms may affect CHD risk biomarkers differently in men and women and also in individuals with and without clinical depression. The *objective* of this aim is to explore the role of these individual characteristics in biomarker responsiveness to PTSD symptom changes. To obtain the objective of this aim, we will test the *working hypothesis* that the association between PTSD symptom severity changes and CHD risk biomarkers will be moderated by individual difference characteristics, including gender and current major depressive disorder. This aim is exploratory yet important for understanding whether gender and depression act as moderators of the effects of PTSD symptom changes on CHD biomarkers of risk. The rationale for this aim is that successful completion of the proposed research will inform clinicians which patients are likely to show the most improvement in CHD risk pathways following PTSD treatment.

Approach. A number of individual characteristics may impact the degree of PTSD symptom response to CPT-C and the associated changes in CHD risk biomarkers observed following CPT-C. *Gender* was selected as a moderator of CHD biomarker response to PTSD symptom changes because of gender differences in PTSD chronicity, behavioral coping strategies to trauma, and compliance with treatment. A stronger CPT-C response might also be anticipated in women because they are more likely to use avoidance and disengagement to cope with prior trauma rather than responding with hostility and excessive substance abuse (Kemp, Hovanitz, & Rawlings, 1995). Although PTSD is associated with increased rates of smoking and alcohol consumption in both men and women, there is some evidence that smoking and alcohol consumption explain more of the CHD risk in men than in women with PTSD (Boscarino, 2008; Kubzansky et al., 2009). *Comorbid major depressive disorder* was selected as a moderator because

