Analytic strategy. We will examine whether the effect of PTSD symptom severity changes on change in CHD risk biomarkers is moderated by patient characteristics of gender and major depressive disorder using the summary measure of PTSD symptom severity change that we defined in AIM 2 and the evaluating the outcome of the participants' post-treatment change in CHD risk biomarkers. We will fit a linear model including the predictors: PTSD symptom severity change, and the PTSD symptom severity change arm by moderator variable interaction (gender of major depressive disorder status) with the addition of covariates for baseline demographic and clinical characteristics. We will estimate 95% confidence intervals from these models for the difference in changes in CHD risk markers for PTSD symptom severity level changes by gender and depression status. As outlined in the section describing more detailed methodologies (C.4), the proposed design will also allow us to explore the role of a number of other patient characteristics as potential moderators of the association between change in PTSD symptom severity and change in CHD risk biomarkers (clinical anxiety disorder, socioeconomic status, and social support).

Potential Difficulties/Alternative Approaches. We anticipate that some participants will drop out of trauma focused therapy (CPT-C). In randomized clinical trials of CPT, drop-out rates have been 20-25% ([name], Nishith, Weaver, Astin, & Feuer, 2002; Chard, 2005). However, this is not likely to compromise our analytic approach for the following reasons: (i) we have structured our compensation system so that financial compensation is contingent upon completion of the PTSD and CHD biomarker

assessment, and not contingent upon completion of the full CPT-C treatment or control arm, and we will encourage participants who cease therapy to remain in the study to complete follow-up assessments; (ii) our analytic approach incorporates methods that are robust to incomplete data. In our recent study examining cardiovascular health risk biomarkers among younger adults with and without PTSD that included multiple laboratory sessions and measurement of 24-hour HRV our attrition rates were less than 10%.

B. METHODS

Participants

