The Fagerström Test of Nicotine Dependence (Heatherton, Kozlowski, Frecker, & Fagerström, 1991) and a smoking history questionnaire (e.g., number of cigarettes smoked/day, age of first smoking, number of previous quit attempts) will be used to measure smoking behaviors. Self-reported alcohol use will be assessed with the three-item Alcohol Use Disorder Identification Test (AUDIT-C; Bush, Kivlahan, McDonnel, Fihn, & Bradley, 1998). We will measure habitual physical activity using the Stanford 7-day physical activity recall interview (Blair et al., 1985). We will measure hostility using a short 27-item form of the Cook-Medley Hostility Scale (CM; Cook & Medley, 1954). The CM has shown high test-test reliability and a number of studies have supported its construct validity as a measure of hostility (Barefoot & Lipkus, 1993). We will measure social support using the Perceived Social Support Scale (PSSS), a 12-item self-report scale that assesses perceived availability and level of satisfaction with support. Socioeconomic status (SES) will be estimated by combining total years of education with income to derive a global socioeconomic status measure (Nam & Powers, 1987). Exploratory analyses will consider the possibility of a moderating role for smoking, alcohol abuse, habitual sedentary behavior, social support, and SES in the association between PTSD symptom change and change in biomarkers of CHD risk. We will also evaluate whether the change in anxiety or depressive symptoms

estimated using the HADS scores act to mediate the association between CPT-C and the proposed improvement in CHD risk biomarkers.

During the screening session, some measures will be completed in the office. Participants will be given the option to complete all measures in the office, or if they prefer, they can take a subset of questionnaires with them to complete at home at their convenience. Any questionnaires that leave the Duke premises will be deidentified. Participants who choose to take questionnaires home will be asked to return them to the study coordinator at their baseline assessment.

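### The Aim 3 moderator model omits treatment arm, and does not clearly contain the moderator main effect for the further exploratory moderators

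*Combined protocol and SAP*

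**What the plan says.** Aim 3, Analytic strategy, defines the model in one sentence: "We will fit a linear model including the predictors: PTSD symptom severity change, and the PTSD symptom severity change arm by moderator variable interaction". The moderators in that sentence are gender and major depressive disorder, as in the aim's hypothesis ("moderated by individual difference characteristics, including gender and current major depressive disorder"). The sentence then continues "with the addition of covariates for baseline demographic and clinical characteristics". No covariate list is attached. The results are to be reported as 95% confidence intervals by gender and depression status.

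The same paragraph adds further candidate moderators: "clinical anxiety disorder, socioeconomic status, and social support". The Measures section (Medications, Health Risk Behaviors, and Psychosocial Assessments) plans exploratory analyses of "a moderating role for smoking, alcohol abuse, habitual sedentary behavior, social support, and SES".

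Two other places bear on the reading:

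- General Analytic Strategies lists "baseline demographic (age, gender, veteran/civilian status) or clinical (high blood pressure, diabetes, major depression) characteristics" in connection with baseline imbalance and possible sensitivity analyses.
- The Aim 2 outcome model has treatment and symptom change as separate terms, and its adjusters are named: "The model will also be adjusted for stratification variables of gender, age, and major depressive disorder".

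**The concern.** Two terms are at issue, with different consequences.

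**Treatment arm.** CPT-C is used to move symptoms, so arm and symptom change are correlated by design. If CPT-C also affects a biomarker by another route, a model without arm assigns that effect to symptom change. The protocol allows for other routes: Aim 2 keeps treatment in its outcome model, and the Measures section plans to test change in anxiety or depression as mediators. The symptom slope within each moderator level is what Aim 3 estimates, and it would be confounded.

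**Moderator main effect.** Symptom change will not average zero. A model with symptom change and its interaction, but no moderator main effect, forces both groups to the same biomarker change at zero symptom change. Any real difference between groups is then pushed into the interaction.

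The phrase about a change arm by moderator interaction adds a further ambiguity. It could be a slip, or it could mean a term involving arm. Aim 3 is meant to tell clinicians which patients gain most, so analysts should not be able to fit materially different models from the same sentence.

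**Working it through.** The plan gives no power or error rate for Aim 3, so there is no stated figure to reproduce.

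**Inputs from the documents.** 120 randomized, 80 to CPT-C and 40 to control, 20% attrition (Power Analysis): 120 × 0.8 = 96, split 64 and 32. Gender is planned at 50/50 (Participants), giving 48 per level.

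**Assumptions not in the documents.** Mean symptom improvement is 18 points (CPT-C) and 4 points (control), within-arm SD 14. Residual SD of biomarker change is 1. There is no true interaction, and tests are two-sided at 5%.

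**1. Arm omitted: bias in the slope.** In units of 14 points, the arm difference in symptom change is (18 − 4)/14 = 1.0. The variance of the arm indicator is (2/3)(1/3) = 0.222. Total variance of symptom change is 1 + 1.0² × 0.222 = 1.222. By the omitted-variable formula,

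bias = δ × (1.0 × 0.222)/1.222 = 0.182 δ,

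where δ is the direct arm effect in SD of biomarker change.

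| δ | Bias per 14 points | Bias per total SD (× √1.222 = 1.106) |
|---|---|---|
| 0.3 | 0.055 | 0.060 |
| 0.6 | 0.109 | 0.121 |

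The standard error of a slope in one moderator level is about 1/√(48 × 1.222) = 0.131. The bias is therefore 0.055/0.131 = 0.42 or 0.109/0.131 = 0.83 standard errors. Nominal 95% intervals would cover about Φ(1.54) − Φ(−2.38) = 93% or Φ(1.13) − Φ(−2.79) = 87%. For a single slope pooled over moderator levels, simulation made a null slope significant in about 9% (δ = 0.3) and 21% (δ = 0.6) of trials, against about 5% with arm included.

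**2. Arm omitted: effect on the interaction test.** A separate simulation used an arm difference of 0.8 SD in symptom change. With a common direct arm effect of 0.5 SD the interaction was rejected in 5% of trials. With unequal symptom response by moderator and direct effects up to 0.8 SD, the rate was 4.5% to 5.7%. It rose to 6.4% only when the direct arm effect itself differed by 0.5 SD between moderator levels (moderator main effect in the model).

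**3. Moderator main effect omitted.** Mean symptom improvement is (64 × 18 + 32 × 4)/96 = 13.3 points, or 0.952 units. With a common intercept, equal groups and a true gap m in biomarker change, the spurious interaction is

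m × 0.952/(0.952² + 1.222) = 0.447 m.

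| Gap m (SD) | Spurious interaction | Rejection, main effect out | Rejection, main effect in |
|---|---|---|---|
| 0.2 | 0.09 | 9–10% | about 5% |
| 0.35 | 0.16 | 18–19% | about 5% |
| 0.5 | 0.22 | 32–35% | about 5% |

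The ranges span separate simulation runs.

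**4. Where the main effect may be missing.** Gender and major depression appear in the General Analytic Strategies list. Clinical anxiety disorder, SES, social support, smoking, alcohol abuse and sedentary behavior do not.

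**5. Cost of adding arm.** For a slope in one moderator level, the usable variance falls from 0.5 × 1.222 = 0.611 to 0.611 − 0.111²/(0.222 − 0.111²/0.611) = 0.550. The standard error grows by √(0.611/0.550) = 1.054. Simulation at n = 96 gave about 6%.

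**The case against.** The sentence does not stop at the interaction. It adds baseline demographic and clinical covariates, and the only place that lists such characteristics together includes gender and major depression. Aims 1 and 2 also adjust for both. A reader might infer that the model holds only symptom change and its interaction, so that the gender and depression results are exposed to false moderation. The documents do not support that: on the natural reading both main effects are present and the interaction test stays near 5%. Nor do they support the inference that omitting arm creates false interactions (step 2). Both parts of this objection stand.

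For the further moderators, the plan says only that they will be explored, and the written model is tied to gender and depression. Smoking, substance abuse and physical activity are also named as covariates in the Aim 1 sensitivity analyses. That is fair, but those analyses are not the Aim 3 model, and no other form is given for these moderators.

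The effect sizes are assumed. A direct effect of 0.6 SD with no symptom effect is extreme: it is numerically as large as the 0.60 effect size in the Power Analysis, yet would bypass the hypothesized mediator entirely. For gender, the plan expects biomarker differences to follow from larger symptom improvement, which implies a small residual gap.

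None of this supplies treatment arm, which is not a baseline characteristic.

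**Conclusion.** The omission of arm holds on any plain reading and is inconsistent with Aim 2. Its effect is a biased symptom slope within each moderator level, about 0.06 to 0.12 SD of biomarker change per SD of symptom change for direct arm effects of 0.3 to 0.6 SD. If there is no direct effect, there is no bias.

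The missing main effect is conditional. It matters only where the covariate clause does not supply it, most plausibly for the further moderators, and then the false-moderation rates in step 3 apply.

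All rates rest on assumed symptom changes and effect sizes and show direction and range only. Aim 3 is declared exploratory and no primary or secondary conclusion depends on it, so severity is minor to moderate.

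**What to change.** Write the Aim 3 model out once and apply it to every moderator:

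biomarker change = symptom change (centred) + moderator + symptom change × moderator + treatment arm + stratification variables (gender, age, major depression).

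Replace the change arm by moderator wording with the intended two-way term. If a term involving arm was intended, say so and list its lower-order terms.

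As a sensitivity analysis, add arm × moderator. In the simulation where the direct arm effect differed by 0.5 SD between moderator levels, moderator plus arm still gave 7% false interactions, and this extra term returned it to 5%.

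The cost is one sentence in the plan, one or two more model terms, no new data, and a standard error for the moderator-specific slope about 6% wider under the assumed symptom changes. Including arm does not make the slope a randomized comparison, because symptom change is itself observed after randomization. It removes one known source of confounding.

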research, if they have any problems during the study, or if they have questions about participating in research studies in general. With regards to determination of decision making capacity of potential participants, our laboratory has a standard procedure for determining understanding of the study procedures, risks, and benefits. We utilize this procedure if we have any reason to suspect that the participant may have difficulty in the consent process (e.g., traumatic brain injury impacting cognitive function, active psychotic symptoms). In this procedure, the study coordinator providing the informed consent information evaluates understanding of the procedures at several different time points during the process by asking questions like "Do you understand what we're asking you to do?" and "Do you have any questions about the risks of the study? Can you tell me what you understand the risks to be?" Prior to having a participant sign consent, the study coordinator, who has clinical experience in working with persons with psychotic disorders, may ask the potential participant to outline the study procedures, risks, and benefits so that he can make sure that the participant is aware of them. If the participant is unable to summarize these, he/she will not be allowed to sign the informed consent form, and may be referred for other treatment. No study procedures will begin until informed consent has been obtained.

Consent During COVID-19 Pandemic. During the pandemic stay-at-home orders, study consent will occur via e-consent. We will also review with participants a brief consent addendum that describes 1) how some study procedures will be done remotely, 2) the addition of COVID-19 measures, and 3) other small study differences. Verbal consent to these procedures will be documented with a note to file signed by the staff member obtaining consent.

Screening, baseline and post-intervention assessments will require 7 testing days per subject. A typical schedule for the screening, baseline and post-intervention assessments would be as follows:

- 1. Days 1-3: Medical exam and psychiatric screening, followed by 24-hour urine collectionDay 4: Psychometrics, fasting blood draw, finger and arm blood pressure measurement, baseline FMD assessment, followed by Holter monitoring for one full day and one full night (about 36 hours)
- 2. Day 5: Post-intervention 24-hour urine collection

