Temporary Measures During COVID-19 Pandemic. Given that exposure to COVID-19 stressors and potential trauma may occur during the pandemic, we would like to ask participants to complete measures related to stress, trauma, and coping strategies. Participants will be informed about these new study procedures verbally, and the study team member who informs them will provide a note-to-fil indicating so. Participants can refuse to complete these measures. We will ask ongoing participants to complete these measures at their next study visit or follow-up session. When study enrollment begins again, participants will complete these measures at the screening session. We are adding the CAIR Pandemic Impact Questionnaire (Lang, 2020; https://www.nlm.nih.gov/dr2/CAIR-PIQ scoring.pdf), and another measure, COVID Core Questions, with variables of interest. If a participant endorses any item marked with an asterisk on the COVID Core Questions measure, we will ask them to complete a PTSD Checklist 5 related to that specific event. Finally, we have added a measure designed to evaluate participants' satisfaction with remote study procedures.

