Video recordings of therapy sessions will be made using a Duke-owned iPhone or iPad that is encrypted at levels compliant with FIPS 140-2 standards. The device to be used will be hardened such that only the video recording capability will remain. Video recordings will be moved from the device to the Duke shared server (file path above) as soon as possible after the recordings have been made, and will then be deleted from the mobile device. Any device that is not in use will be stored in a locked filing cabinet in [name] office. Video recordings will remain on the Duke shared drive until the fidelity raters are ready to evaluate them. Copies will then be moved to Box@Duke, where they can be viewed and evaluated by the raters. The recordings will be copied to an encrypted hard drive for permanent storage, and the copies on the Duke shared drive will be deleted. The encrypted hard drive will be stored in a locked file cabinet in [name] or [name] lab space at Duke South. Only the key personnel listed on the staff listing will have access to the encryption password and/or the hard drive.

Participants enrolled during the COVID-19 pandemic may be sent study equipment or study documents via FedEx. If that occurs, FedEx will be provided the name and address of the delivery recipient. No other information (including health information) will be included with the name and address.

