Data Safety and Monitoring Board. This study will also utilize a Data Safety and Monitoring Board (DSMB) to enhance participant protection. Three consultants will serve as members of the Data and Safety Monitoring Board (DSMB) created for this project: 1) [name], University of North Carolina at Chapel Hill, will provide expertise in cardiology; 2) [name], University of North Carolina at Chapel Hill, will provide expertise in mental health; and 3) [name] [name], Dartmouth Institute for Health Policy and Clinical Practice, will provide expertise in biostatistics. The Data and Safety Monitoring Board (DSMB) will review adverse events and monitor the safety of participants and the quality and completeness of the accrued study data during regularly scheduled meetings. The DSMB will convene every year, but is consulted at any time in the event of study-related, unanticipated and/or serious adverse events. The DSMB performs the critical function of monitoring all studies for adverse events and determining whether a favorable risk-benefit ratio justifies continuation of a given study. The DSMB plays a complementary role to the Duke University IRB, which focuses mainly on the prospective review of study protocols (although the IRB may also be involved in halting a study in the face of serious, reportable adverse events). Decisions of the DSMB are made by majority vote, with the results of each vote and relevant discussion recorded in the meeting minutes (which, after circulation and emendation, are approved by each member).

Additional Information Regarding Data Analyses

Power Analysis. The sample size estimate of n=120 subjects (80 in the CPT-C arm and 40 in the control arm) is based on a 2:1 randomization and the AIM 1 comparison of HRV improvement between CPT-C and control arms at 6 weeks. For sample size calculations we used methods appropriate for ANCOVA type analyses (Borm, Fransen, & Lemmens, 2007), which are equivalent in terms of efficiency to our linear model for randomized trials (Fitzmaurice, Laird, & Ware, 2004). Quantities needed for this sample size calculation include the baseline standard deviation and the correlation between baseline and follow-up. As we have limited pilot data, we

Table 2. Effects size and mean differences of HRV detectable with 80% power in 120 randomized subjects.

Correlation	Standard	Effect Size	Mean
(rho)	Deviation	Difference	HRV
			difference
0.30	40	0.60	24.0
0.30	50	0.60	30.0
0.40	40	0.55	22.0
0.40	50	0.55	27.5

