0.50	40	0.55	22.0
0.50	50	0.55	27.5
0.60	40	0.50	20.0
0.60	50	0.50	25.0

assumed a range of correlations between 0.3 and 0.6 and standard deviations (SD) of 40 and 50. **Table 2** presents effect size differences with 120 subjects. Using the most conservative assumptions, with 80% power, alpha=0.05, SD=50, rho=0.3, and 20% attrition rate by 7-weeks we can detect an effect size difference of 0.60 (Cohen, 1988), corresponding to a difference of 30 units in mean HRV levels at 7-weeks between CPT-C and control. For the AIM 2 mediation analysis, we will test that the effect of CPT-

C on CHD biomarkers is attributable to changes in PTSD severity. We determined detectable effect sizes for mediation based on empirical power estimates for the product-of-coefficient test (i.e., the product of γ_1 and β_2) given by Fritz and MacKinnon (2007). With 120 subjects and a type-I error of 0.05, we will have 80% power to detect medium to large effect size differences for each of the parameters individually (e.g, γ_1 and β_2) that are part of the product test.

Missing Data. Our plans for preventing and dealing with missing data follow the guidelines set forth by the National Research Council's Panel on Handling Missing Data in Clinical Trials. First, , we have numerous strategies in place to prevent attrition; based on prior experience with a similar design and population, we anticipate that we will have less than 20% attrition. Second, as recommended by the panel, we will conduct two general types of sensitivity analyses for our primary analysis. If the missing values are related to measured factors, such as treatment group or baseline comorbidities, then multiple imputation will be used to incorporate information for these auxiliary variables while still preserving a parsimonious main treatment effect model (Collins, Schafer, & Kam, 2001). As a first sensitivity analysis, we will construct a general, multivariate imputation model using all observed CHD markers, treatment group, and any covariates predictive of missingness (Olsen, Stechuchak, Edinger, Ulmer, & Woolson, 2012). The primary analysis models will then be fit to the multiply imputed data and the estimates and standard errors will be combined using appropriate combining rules. We acknowledge the possibility that data may be missing not at random and propose as a second sensitivity analysis to explore pattern-mixture models and the toolkit of methods recently advocated by O'Kelly and Ratitch (2014).

References

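### The Aim 2 mediation model and the Aim 3 subgroup slopes carry no pandemic-period term, so a pandemic that moved both symptom change and biomarker change would confound them by an amount the documents do not let us size

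*Combined protocol and SAP*

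**What the plan says.** Three places describe the pandemic. Temporary Measures During COVID-19 Pandemic gives as its reason "Given that exposure to COVID-19 stressors and potential trauma may occur during the pandemic" and adds pandemic questionnaires, which participants may decline. It also shows that some people were already in the trial: "We will ask ongoing participants to complete these measures at their next study visit or follow-up session". Consent During COVID-19 Pandemic introduces an addendum on "how some study procedures will be done remotely", without naming the procedures. Data Storage and Security says "Participants enrolled during the COVID-19 pandemic may be sent study equipment or study documents via FedEx".

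None of this reaches the analysis. Randomization is stratified by gender, age and major depressive disorder (MDD).
- **Aim 1** models time and arm by time, adjusts for the strata, and in sensitivity analysis adds comorbidity, smoking, substance abuse and physical activity.
- **Aim 2** regresses biomarker change on arm and on symptom change C from week 0 to week 6. Of adjustment it says: "The model will also be adjusted for stratification variables of gender, age, and major depressive disorder". Its sensitivity analysis leaves room for further covariates but names only changes in HADS anxiety and depression.
- **Aim 3** uses symptom change, its interaction with gender or MDD, and baseline characteristics.

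The Missing Data section names no period or visit-mode variable either.

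**The concern.** Randomization protects comparisons between arms. It does not protect the slope of biomarker change on symptom change, because nobody is randomized to a symptom change. That slope, beta_2, has a causal reading only if nothing outside the model drives both changes. The protocol itself describes a candidate: a period of new stress and possible trauma, which could raise PTSD scores and also affect autonomic and inflammatory measures. If it acted on both changes, Aim 2 could report mediation that partly reflects calendar time. This matters because the protocol presents the link between symptom change and biomarker change as its main goal.

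The people most exposed are those whose baseline came before the pandemic and whose follow-up came during it, since their two assessments were made under different conditions.

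**Working it through.** **1. The plan's own figure.** Power Analysis gives "n=120 subjects (80 in the CPT-C arm and 40 in the control arm" and "80% power, alpha=0.05, SD=50, rho=0.3, and 20% attrition rate by 7-weeks". After 20% attrition, 64 and 32 remain, or 96 completers. With two-sided alpha (assumed; sidedness is not stated) and the ANCOVA factor, the detectable effect is

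d = √(1 − 0.3²) × (1.960 + 0.842) × √(1/64 + 1/32) = 0.954 × 2.802 × 0.2165 = 0.579.

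The plan states an "effect size difference of 0.60", which agrees on the table's 0.05 grid. The sample-size basis is not in dispute, and 96 is the N used below.

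**2. Bias formula.** Let a share p of completers have symptom change shifted by dM and biomarker change by dY, in residual SD units. With period omitted and a true beta_2 of zero, the spurious slope has magnitude

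p(1 − p)·dM·dY / (1 + p(1 − p)·dM²).

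At p = 0.30 and both shifts 0.5: 0.21 × 0.25 / (1 + 0.0525) = 0.050. At p = 0.30 and both 0.8: 0.21 × 0.64 / (1 + 0.1344) = 0.118.

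**3. Simulation of the Aim 2 equations.** N = 96, true beta_2 = 0, arm effect on symptom change 0.8 SD (assumed), strata omitted. There were 20,000 trials per cell for shares of 10% and above, and at least 6,000 for the 3–7% rows. Share and shift are assumptions throughout. The joint test requires both gamma_1 and beta_2 to be significant.

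| Share affected | Shift in both changes | Spurious slope (magnitude) | beta_2 test | Joint test | First-order Sobel |
|---|---|---|---|---|---|
| none | – | 0 | 4.9% | 4.7% | 2.0% |
| 3–7% | 0.5 SD | 0.007–0.016 | 5.0–5.6% | – | about 2% |
| 3–7% | 0.8 SD | 0.02–0.04 | 5.2–6.6% | – | 2–3% |
| 10% | 0.5 SD | 0.022 | 5.4% | 5.1% | 2.3% |
| 20% | 0.5 SD | 0.038 | 6.5% | 6.1% | 2.8% |
| 30% | 0.5 SD | 0.050 | 7.3% | 7.0% | 3.1% |
| 30% | 0.8 SD | 0.118 | 20.8% | 19.2% | 10.2% |
| 50% | 0.8 SD | 0.138 | 26.6% | 24.4% | 13.1% |

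At a 0.3 SD shift the beta_2 rate stays at 5.1–5.5% for every share from 10% to 50%. With a period indicator in the model, the beta_2 test returns to about 5% and Sobel to about 2% in every cell. The standard error of beta_2 rises by less than 2% when the share is 10% or more.

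**4. When there is no bias.** A level shift that is equal at both visits cancels in the change scores. A shift in symptom change alone leaves beta_2 unbiased (4.9% in simulation). The Aim 1 arm contrast has mean bias of about zero and a rejection rate near 5%, with or without the term.

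**5. How many might straddle.** The documents do not say. As an illustration only, assume even accrual of 120 over 60 months (Recruitment refers to years one through five), or 2 a month. With 2 to 3.5 months between T1 and T2 (the CPT-C description allows a 12-week course), 4 to 7 participants straddle. That is 4/120 = 3% to 7/120 = 6%.

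**The case against.** The strongest reply is that the exposed group is probably small. Mediator and outcome are within-person changes over about seven weeks, so someone assessed wholly within the pandemic contributes no bias merely by being in that era; the pandemic would also have to alter both of that person's changes. The straddlers are the clear risk, and enrollment was paused. At 3–7% the false-positive rate barely moves. This stands as a limit on size, but the straddler share rests on assumed even accrual and cannot be confirmed.

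Second, Aim 2 names an extension of the Sobel test for the product gamma_1·beta_2. A first-order Sobel test is conservative here and stays below 5% at a 0.5 SD shift. This stands for the product test. It does not cover the MacArthur criterion, which looks for gamma_1 together with beta_2 or beta_3; the joint gamma_1 and beta_2 test stays close to the beta_2 rates.

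Third, Aim 2's open-ended sensitivity covariates would permit a period term. They would, but they commit to none, so the choice could be made after results are seen.

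Two stronger readings are tempting. A reader might infer that remote delivery changed how the biomarkers were measured. The documents do not show this: the remote procedures and the shipped equipment are not specified, blood draw and blood pressure are placed in the research facility, FMD is hands-on, and Holter and 24-hour urine were already collected away from the clinic. A reader might also infer that the Aim 3 moderation test is biased. A common period effect distorts the slope within each subgroup, but it biases the interaction only if pandemic share or effect differs by gender or MDD. Nothing in the documents shows that it does.

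**Conclusion.** The gap is real and its size is unknown. The Aim 2 model and the Aim 3 subgroup slopes omit a possible common cause that the protocol itself describes, and the slope of interest is not protected by randomization. Confounding requires the pandemic to have moved both changes. If only a few straddlers were affected, the consequence is negligible. It becomes serious only with a large share and a large shift, such as 30% and 0.8 SD, where the beta_2 false-positive rate is about 20% and the Sobel rate about 10%. The documents supply neither input, so those figures mark a range and are not estimates for this trial.

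The primary Aim 1 comparison is not threatened: it is unbiased in expectation, and a period term there would only improve precision. The sample size and Table 2 are unaffected. This is a worthwhile, inexpensive addition to the plan for Aims 2 and 3, not a flaw in the primary analysis.

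**What to change.** Before analysis, define one categorical period covariate from visit dates: both visits before the pandemic, straddling, or both during, with the cut-off date written into the plan. Include it in both Aim 2 equations (mediator and outcome) and in the Aim 3 slope models. Repeat Aims 2 and 3 without straddlers as a sensitivity analysis.

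Use this single covariate instead of separate T1 and T2 indicators, which would be nearly collinear with few straddlers. Base it on dates and not on the pandemic questionnaires, since dates exist for everyone and the questionnaires may be declined. Add a visit-mode term only for measures actually done remotely, after listing which those were. Report the category counts by arm, because the T2 date can depend on the pace of therapy.

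The cost is one derived variable, one or two degrees of freedom and a slightly larger standard error. If few participants straddle, that category's effect will be imprecisely estimated, and the report should say so. No new data collection is needed.
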